June-July 2019, we surpassed our recruitment goal of 200 by recruiting 302 participants. Adjusted general linear and logistic regression models were used to evaluate associations between how long customers had been shopping at the mobile market and fruit and vegetable intake and odds of food insecurity (**Table 2**). We found longer market use was associated with higher fruit and vegetable intake and lower odds of being food insecure, supporting the scientific premise of the proposed study. We also found 85% of customers identified as food insecure and 90% felt their cultural food preferences were met at the market. Results further support proposed trial feasibility.

Table 2. Year 1 Customer Survey (N=302) Outcomes

Aim/Outcome	Length of mobile market shopping
Aim 1a. FV intake ^a	$\beta=0.26$, SE:0.10, p=0.01
Aim 1b. Odds of food insecurity in last year ^b	OR=0.77; 95% CI=0.60-0.997

Notes. Models were adjusted for sociodemographic characteristics. FV=Fruit / vegetable. ^aAssessed with two questions found to rank individuals based on overall FV intake in population-based surveys.¹³⁷ ^bAssessed with a two-item validated measure.¹³⁵ *Manuscript in press at Appetite.*

Point-of-Sales [IRB study number STUDY00000051]. We analyzed mobile market point-of-sales data by food group for 2016.⁵⁹ This data showed half of full-service mobile market sales were for fruits and vegetables, with all food groups contributing to the other half.⁵⁹ This work demonstrates our capacity to collect and analyze key implementation and process data that measure reach, adoption, and maintenance of mobile market shopping.

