3.0 Study Endpoints/Events/Outcomes

3.1 Primary Endpoint/Event/Outcome:

Diet quality. Trained research staff certified in collecting dietary recalls using Nutrition Data System for Research software will collect three 24-hour dietary recall interviews (2 weekdays, 1 weekend day) from each participant at each measurement period (baseline and follow up). Dietary recall data will be used to calculate the Health Eating Index-2015 Score. HEI-2015 is a scoring system designed to measure adherence to the 2015-2020 Dietary Guidelines for Americans (2015-2020 DGA).^{69,70}

3.2 Secondary Endpoint(s)/Event(s)/Outcome(s):

Food insecurity. Food insecurity in the past 6 months will be measured with the gold-standard, 18-item food security screening module of the USDA, which will allow for assessment of both binary food insecurity (yes, food insecure; no, food secure) and level of food security (very low, low, marginal, and high food security).⁹¹ We will also use newly developed and validated nutrition insecurity measures to assess **nutrition insecurity** in the past 6 months, which helps us understand fuller contexts around choices people may make when money is tight (e.g., compromise nutrition for a full stomach).¹³⁷

Fruit & Vegetable purchasing outcomes: Participants will record their fruit and vegetable purchases using forms in a provided booklet, and mail their booklets to the researchers in prepaid addressed envelopes, which will be used to measure:

- Average weekly servings of fruits and vegetables purchased
- Total number of trips
- Store types visited

Mobile Market shopping patterns: Participants randomized to the intervention sites will participate in a “Market Members” program, which tracks their purchases at the Mobile Market (i.e. number of transactions, items purchased, dollars spent).

Personal, social, behavioral, and environmental factors that may influence mobile market adoption. These factors include:

- Neighborhood Healthy Food Availability (4 item scale; $\alpha=0.89$);⁹⁹
- Social Connectedness (8 item scale, $\alpha=0.92$);¹⁰²
- Health-related quality of life (4-items);¹⁰³⁻¹⁰⁷
- Self-efficacy of Healthy Cooking (4 item scale, $\alpha=0.85$).¹⁰⁹
- Self-efficacy for eating and cooking fruits and vegetables (4 item scale, $\alpha=0.90$).¹⁰⁸
- Everyday Discrimination Scale (6 item scale $\alpha=0.77$ + 2 follow-up items)¹³⁹⁻¹⁴⁰

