Food insecurity. Food insecurity in the past 6 months will be measured with the gold-standard, 18-item food security screening module of the USDA, which will allow for assessment of both binary food insecurity (yes, food insecure; no, food secure) and level of food security (very low, low, marginal, and high food security).⁹¹ We will assess for change in prevalence of food insecurity and level of food security from baseline to follow-up (e.g., change in % very low food security from baseline to follow-up), as assessed in other community-based food intervention studies aiming to improve food security.^{97,98} We will also use newly developed and validated measures to assess ***nutrition insecurity*** in the past 6 months, which helps us understand fuller contexts around choices people may make when money is tight (e.g., compromise nutrition for a full stomach).¹³⁷ These measures will be collected via REDCap, which makes the skip patterns invisible and easy for participants.

Fruit & Vegetable purchasing outcomes: Participants will record the fruits and vegetables that they buy along with the date and place of purchase using forms in provided booklets, and mail these booklets to the researchers in prepaid addressed envelopes, which will be used to measure:

Average weekly servings of fruits & vegetables. The purchase quantity (volume, weight, quantity) of fruits and vegetables from the forms will be entered into NDSR. Using these data, NDSR will calculate the edible

servings for each item. This process accounts for and eliminates the inedible portions of foods (e.g., peels, pits). The edible servings purchased will be summed and averaged to obtain the average servings of fruits and vegetables purchased weekly across all purchase locations. See Fruit & Vegetable Purchasing data collection protocol and Fruit & Vegetable purchasing booklets for participants attachments.

Descriptive purchasing variables measured with data from the fruit & vegetable forms. Total number of trips and store types visited will be measured using the data from the fruit & vegetable forms. See the Fruit & Vegetable Purchasing Data Collection Protocol and Fruit & Vegetable purchasing booklets for participants attachments.

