17.0 Statistical Considerations

17.1 Data Analysis Plan: See section 17.3

17.2 Power Analysis:

Power calculation. For the primary outcome of change in HEI scores, power is computed based on a t-test at the individual client level, but the sample size is inflated for the group randomization design by a factor of $1+(m-1)*ICC$ where m is the average cluster size and ICC is the intraclass correlation. In Co-Investigator [name]'s study with participants similar to the proposed study (i.e., from the same communities with similar income and diversity levels), the HEI SD was 11.2.⁹⁰ In our preliminary customer intercept survey study, we found an ICC of 0.0004. Therefore, to be conservative, we assume an SD of 12 and an ICC of 0.01. Under these assumptions with a two-sided type I error rate of 5%, this study will have 80% power to detect a mean difference of 5.5 HEI points between intervention and control participants with an average cluster size m of 20 and number of clusters k of 12 for a total of 264 participants (132 per group). This calculation assumes an attrition rate of 20%. Detection of a 5.0 point difference in HEI is clinically significant, as it corresponds to a lower risk of cardiovascular mortality and lower risk of all-cause mortality.¹²² Additionally, given our conservative approach, we may ultimately be adequately powered to detect even smaller differences in HEI scores between intervention and control sites.

17.3 Statistical Analysis:

Aim 1: The primary analysis will compare the mean within-person, baseline to follow-up change in HEI-2015 between the mobile market and waitlist control groups. Changes in HEI-2015 will be modeled via a Generalized Estimating Equation (GEE) linear model to account for the possible correlation of outcomes within community sites. Food insecurity, as measured by the U.S. Adult Food Security Survey Module, will be analyzed similarly. Baseline characteristics of randomized

SOCIAL PROTOCOL (HRP-580)

PROTOCOL TITLE: Mobile Food Market Cluster Randomized Trial

VERSION DATE: 1/5/2023

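### Food insecurity: the only model the plan points to is a linear change score without baseline status as a covariate, which is unbiased but less precise than it could be

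*Combined protocol and SAP*

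**What the plan says.** Section 17.3 (Aim 1) sets out the HEI-2015 analysis in two sentences. The contrast is: "The primary analysis will compare the mean within-person, baseline to follow-up change in HEI-2015 between the mobile market and waitlist control groups". The estimator is: "Changes in HEI-2015 will be modeled via a Generalized Estimating Equation (GEE) linear model to account for the possible correlation of outcomes within community sites". For the secondary outcome there is one sentence: "Food insecurity, as measured by the U.S. Adult Food Security Survey Module, will be analyzed similarly". No link function, ordinal model or baseline outcome covariate is named for it.

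The outcome itself is categorical. Section 3.2 says the USDA module allows "assessment of both binary food insecurity (yes, food insecure; no, food secure) and level of food security (very low, low, marginal, and high food security"). Section 5.2 adds: "We will assess for change in prevalence of food insecurity and level of food security from baseline to follow-up", and gives the change in the percentage with very low food security as its example. Section 1.1 words Hypothesis 1b as a difference between groups at follow-up.

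Two provisions bear on baseline balance. Section 17.3 goes on to say that baseline characteristics will be summarised and imbalanced variables adjusted for where this is judged necessary. Section 9.1 stratifies the randomization of sites by site type. The data collection table in section 5.2 shows food security measured at both baseline and follow-up.

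**The concern.** A yes/no status gives a change of -1, 0 or 1. Someone insecure at baseline can only stay the same or improve, and someone secure can only stay the same or worsen, so the change is tied to the starting value. A change score subtracts the whole baseline value, which is the best weight only if status is almost perfectly stable over time. At any lower correlation it subtracts too much and adds noise.

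Two things follow for Hypothesis 1b. The confidence interval is wider than the data require. And if the 6 intervention and 6 control sites happen to differ in baseline prevalence, the estimate moves the opposite way by more than it should. Section 17.3 puts its emphasis on confidence intervals rather than tests, so interval width matters here.

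**Working it through.** **The plan's own figures.** Sections 11.1 and 17.2 give sample size and power for HEI-2015 only, so there is no food insecurity figure to reproduce. As a check on the inputs borrowed below: SD 12, 224 analysed, 12 sites and ICC 0.01 give a design effect of 1 + (224/12 - 1) × 0.01 = 1.177 and 82% power at 5.0 HEI points. That agrees with the 80% in section 11.1.

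**Inputs.**
- Analysed n = 224, 12 sites (section 11.1).
- ICC 0.01: stated for HEI-2015, assumed here for food insecurity.
- Baseline prevalence: 85% from the intercept survey (section 2.2: "We also found 85% of customers identified as food insecure"), or 67% among non-customers recruited from waitlist sites (section 2.2, Table 1). The second group is closer to the people this trial will enrol. Both figures come from a two-item screener, not the 18-item module.
- Correlation r between baseline and follow-up status: not in the documents; assumed 0.3, 0.5 and 0.7.

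**Step 1. Variance ratio.** With variance s² at each time, the change score has variance 2s²(1 - r) and the baseline-adjusted outcome has s²(1 - r²). The ratio is (1 - r²) / [2(1 - r)] = (1 + r)/2.

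| r | Change score (× s²) | Adjusted (× s²) | Ratio |
|---|---|---|---|
| 0.3 | 1.40 | 0.91 | 0.65 |
| 0.5 | 1.00 | 0.75 | 0.75 |
| 0.7 | 0.60 | 0.51 | 0.85 |

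**Step 2. Size of a chance baseline gap.** SE = sqrt(4p(1 - p)/n × design effect).
- p = 0.85: sqrt(4 × 0.85 × 0.15 / 224 × 1.177) = 0.052, or 5.2 points.
- p = 0.67: sqrt(4 × 0.67 × 0.33 / 224 × 1.177) = 0.068, or 6.8 points.

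On a normal approximation, a gap above 10 points has a chance of about 5% at 85% prevalence and 14% at 67%. With the 20% attrition of section 17.2 (264 × 0.8 = 211 analysed) the SEs are 5.3 and 7.0 points. Over assumed ICCs of 0.0004 to 0.05 with n = 224 they run from 4.8 to 6.5 points (85%) and from 6.3 to 8.6 points (67%).

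**Step 3. Over-correction.** Given a gap, the unadjusted change estimate moves by (1 - r) × gap in the opposite direction. At r = 0.5, a one-SE gap moves it by 0.5 × 5.2 = 2.6 points (85%) or 0.5 × 6.8 = 3.4 points (67%).

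**Step 4. The shift is not additional to Step 1.** 2(1 - r) = (1 - r²) + (1 - r)². The second term is the variance due to over-correction, so the shift is already inside the variance ratio and inside the reported interval. At r = 0.5 the change estimate has an SE of sqrt(1.00) × 5.2 = 5.2 points at 85%, so the 2.6-point shift is half an SE. The adjusted SE would be sqrt(0.75) × 5.2 = 4.5 points.

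**Step 5. Simulation with a binary outcome.** This used 12 sites of 19, ICC 0.01, a site-level t-test with 10 df and 4,000 runs per setting. With no effect, the change score showed no average bias and rejected in 4.9% to 5.8% of runs. With an assumed 15-point fall in food insecurity, power was:

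| Baseline prevalence | r | Change score | Baseline-adjusted |
|---|---|---|---|
| 67% | 0.3 | 0.42 | 0.56 |
| 67% | 0.5 | 0.52 | 0.62 |
| 67% | 0.7 | 0.68 | 0.76 |
| 85% | 0.3 | 0.57 | 0.70 |
| 85% | 0.5 | 0.67 | 0.77 |
| 85% | 0.7 | 0.80 | 0.84 |

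**The case against.** The sponsor can fairly reply on four points.

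- **The plan does not state a linear change model for this outcome.** A reader might infer that the four levels will be scored as equally spaced and entered in a linear model. The documents do not say so: GEE also covers binary outcomes, and section 5.2 speaks of prevalence and of the percentage with very low food security, which are proportions. If a linear GEE on change in a 0/1 status is what is meant, it estimates a difference in change in prevalence, which is a legitimate target. This stands. What remains is that the only model the text gives is the linear change score, and no baseline covariate is named under any reading.
- **The baseline value is not discarded.** A change score uses it, with a fixed weight of 1. This stands; the loss is one of efficiency.
- **The contrast is not biased.** A reader might take the 2.6-point shift as bias on top of lost precision. Steps 4 and 5 show it is neither a bias nor additional.
- **Imbalance is provided for.** Section 17.3 allows adjustment, and in a linear model adding baseline status to the change-score regression gives the same treatment coefficient as modelling follow-up adjusted for baseline. Applied to baseline food insecurity, that clause would yield the recommended analysis. Section 9.1 also stratifies by site type. This stands in part: the adjustment is decided after seeing the data, has no stated threshold, does not name the baseline outcome, and recovers no precision when the groups happen to be balanced. Stratification by site type does not fix baseline prevalence.

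**Conclusion.** The concern holds as a modest inefficiency together with an unstated model. Adjusting for baseline status would cut the variance of the treatment contrast by 35%, 25% or 15% at r of 0.3, 0.5 or 0.7.

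The formula assumes equal variances at the two times. The correlation, the ICC for this outcome, the baseline prevalence and the 15-point effect in the simulation are all assumptions, because the documents give none of them for the 18-item module in this population. The direction does not depend on them: with equal variances the ratio is below 1 for every r below 1.

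The documents do not support a finding that the planned comparison is invalid or unprotected against imbalance. Because the outcome is secondary, this is a worthwhile improvement and not a condition for going ahead.

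**What to change.** In section 17.3, replace the single sentence on food insecurity with a named model for each measure.

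- **Binary status:** a site-clustered GEE for follow-up food insecurity, with treatment group and baseline food insecurity as pre-specified covariates whatever the observed balance. Report the marginal risk difference with its confidence interval.
- **Four levels:** analyse the category proportions that section 5.2 already has in view, such as the percentage with very low food security, adjusted for baseline level. An ordinal model is optional.

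Keep the existing clause on imbalanced variables for other characteristics, and state that the baseline value of the outcome is not subject to it. The cost is a wording change in one section. Food security is already collected at both times, so no data collection changes.

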Fruit & Vegetable form completion for 4 weeks		x		x	
Personal, social, behavioral, and environmental factors survey		x		x	
Demographics		x			
Randomization**		x			
Adverse Events		x	x	x	
Mobile market shopping purchases (intervention participants only)			x		
Quantitative measures of mobile market factors that may influence shopping adoption (intervention participants only)				x	
Qualitative interviews with a subset of intervention participants (high & low adopters)					x
Process measures			x	x	

** Randomization occurs after site recruitment for the Wave is complete (about 2 months prior to the end of data collection for the wave. Sites (and the participants attached to those sites) will be randomized to receive mobile market service or to the waitlist (to receive mobile market service after data collection for the wave is complete). After randomization, the study statistician will be unblinded to site names by being provided access to the key that matches sites with their assigned numbers. This will inform him which sites were randomized to the intervention and waitlist control. The study statistician will inform the mobile market co-investigator of the sites randomized to the intervention approximately 2 months prior to the end of data collection to allow time for the mobile market to plan for market routes and schedules. Participants, site locations, the PI, and other UMN trial investigators and staff will be blinded to (i.e., not be informed of) site randomization results until after baseline data is collected. The mobile market co-investigator will explicitly instruct the market drivers (who will help plan the routes with the new stops for the trial sites) that the knowledge of sites is strictly confidential until after baseline data collection is complete and contact between mobile market staff (aside from the Mobile Market co-investigator) and research team, PI, and University staff will not occur during this time to reduce any potential for unintentional disclosure.

Diet quality will be measured through 24-hour dietary recall interviews. Trained staff certified in collecting diet recalls using Nutrition Data System for Research (NDSR) will collect three 24-hour recall interviews (2 weekdays, 1 weekend day)

SOCIAL PROTOCOL (HRP-580)

PROTOCOL TITLE: Mobile Food Market Cluster Randomized Trial

VERSION DATE: 1/5/2023

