11.0 Number of Participants

11.1 Number of Participants to be Consented:

Targeting enrollment at 264 participants in full-data collection.

For qualitative interviews, these will happen with a smaller subsample of participants enrolled. Specifically, the qualitative sample will be derived from purposive sampling of extremes^{119,120} in market adoption. Thus, participants selected for interviews will be from the highest and lowest quintiles of market shopping as measured by the number of trips to the Mobile Market during the final two months of the intervention period. The estimated number of interviews is 24 for low adopters and 24 for high adopters (48 total) selected from across intervention sites,¹²¹ however, the qualitative sample size will only be set after saturation has occurred during analysis and coding of the qualitative data.¹²¹

For our primary outcome, with our planned sample size of 264 divided between 12 clusters, we anticipate 80% power to detect a difference of 5.0 HEI points between the intervention and control groups. This calculation assumes an attrition rate of 15%, so that our final analytic sample size is 224 individuals, and a conservative ICC of 0.01. If attrition is higher or recruitment is slower, a final analytic sample of n=160 individuals will provide 80% power to detect a difference of 6.0 HEI points, which is still within the range of plausibility for the effect size of this intervention.

Furthermore, smaller effects will be detectable even with this smaller sample if the ICC is closer to the value 0.004 observed in previous studies. Additionally, for our secondary outcomes, an even smaller sample would be acceptable for analysis. For example, for the third aim, we are aiming for 24 high mobile market shopping adopters and 24 low mobile market shopping adopters (final sample size will be determined once saturation is reached).

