groups will be summarized to assess whether any chance imbalances between groups are scientifically meaningful. If necessary, imbalanced variables will be adjusted for in outcome analyses. For variables with > 10% missing values, we will compare characteristics between individuals with missing and non-missing values and perform multiple imputation if needed.¹²³ Since several hypotheses on different outcomes are of interest, we will focus mainly on reporting confidence intervals rather than null hypothesis significance testing, an approach in line with current recommendations.¹²⁴ If the overall intervention effect is sufficiently large (i.e., of similar clinically meaningful size that we are powered to detect), we will use exploratory analyses to assess the presence and magnitude of possible treatment-covariate interactions, where again the focus will remain on identifying interactions of a clinically meaningful magnitude rather than those that achieve a pre-determined significance threshold. In particular, we will investigate the influence of sex as a biological variable by assessing whether intervention effects vary by sex. While the primary analyses will be conducted within an intent-to-treat (as randomized) framework, we will also perform dose-adjusted analyses to investigate the association between frequency and volume of use of the mobile market and the outcomes of interest, and whether these usage measures mediate the effects of the intervention.¹²⁵ For process and implementation measures taken at the site level, the focus will be mainly on creating meaningful descriptive statistics and visualizations.

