Aim 2: The main purchasing outcomes will be the average number of servings of fruits and vegetables purchased each week. These outcomes will be treated as continuous variables and modeled using mixed effects regression models with random effects for participant, site, and time. Initially, we will fit separate models for each outcome (average fruit, and vegetable servings purchased each week); we will also consider joint outcome models that use the vector of servings (fruit, vegetables) as the outcome. These models will be used to assess whether temporal trends in food purchases are different between study groups, and whether any differences in trends identified are modified by other baseline covariates, including sex as a biological variable. If any outcomes are zero-inflated, we will consider regression models which accommodate this, e.g., negative binomial regression. Similar approaches will be used to analyze intervention effects on other purchasing outcomes. Further, we will perform exploratory analyses to identify trends and patterns in intervention site participant mobile market purchases (tracked with customer loyalty cards) over the 6 month intervention period.

Aim 3: Quantitative statistical procedures and analysis. We will use mixed effects (i.e., repeated measures) models similar to those in Aim 2 to quantify associations between personal, social, environmental, and behavioral factors and the quantitative shopping adoption outcome measures for intervention group participants. We will construct both univariate and multivariate models to consider the independent and joint effects of each of these explanatory factors, along with exploring other potential predictors of shopping adoption (e.g., sociodemographic

SOCIAL PROTOCOL (HRP-580)

PROTOCOL TITLE: Mobile Food Market Cluster Randomized Trial

VERSION DATE: 1/5/2023

characteristics, dietary quality, food insecurity). We will also perform additional analyses to quantify joint associations between baseline factors, shopping adoption, and perceived mobile market features at follow-up.

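### The only model named for zero-inflated purchase outcomes, negative binomial regression, has no zero component and does not suit a continuous weekly average

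*Combined protocol and SAP*

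**What the plan says.** Section 17.3 (Aim 2) of the combined protocol and SAP defines the outcome: "The main purchasing outcomes will be the average number of servings of fruits and vegetables purchased each week". The default analysis follows: "These outcomes will be treated as continuous variables and modeled using mixed effects regression models with random effects for participant, site, and time". Fruit and vegetables are first modelled separately, with a joint model to be considered. The fallback is one sentence: "If any outcomes are zero-inflated, we will consider regression models which accommodate this, e.g., negative binomial regression".

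Section 5.2 explains how the outcome is built: "The edible servings purchased will be summed and averaged to obtain the average servings of fruits and vegetables purchased weekly across all purchase locations". The schedule table in the same section gives the recording period at baseline and at follow-up: "Fruit & Vegetable form completion for 4 weeks".

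The Aim 1 paragraph of section 17.3 says of inference that "we will focus mainly on reporting confidence intervals rather than null hypothesis significance testing".

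The plan does not say when an outcome counts as zero-inflated, which type of standard error the fallback would use, on which scale its effect would be reported, or whether the participant, site and time effects would carry over.

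**The concern.** The sentence offers negative binomial regression as a model that accommodates zero inflation. That model handles overdispersion. Excess zeros have nowhere to go except into its dispersion parameter, which then no longer describes the variability of the purchases. It is also a model for whole-number counts, whereas the plan averages edible servings over four weeks and calls the result continuous.

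Reporting rests mainly on confidence intervals, so what is at stake is whether those intervals have the right width and refer to a contrast fixed in advance. The default mixed model gives a difference in mean servings. A negative binomial model with its usual log link gives a ratio. As written, the look of the data decides which is reported.

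The fallback could be needed. Splitting fruit from vegetables makes zeros more likely than in a combined total, and Aim 3 uses similar models for shopping adoption, where non-shoppers spend nothing at the market.

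**Working it through.** **Inputs from the plan.** The outcome is an average over four weeks (sections 5.2 and 17.3). There are 12 sites (section 5.1). Section 11.1 says: "This calculation assumes an attrition rate of 15%, so that our final analytic sample size is 224 individuals". That is 112 per arm. Section 17.2 uses 20% attrition instead, but sample size cancels from the ratio below.

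**Inputs the plan does not give.** There is no mean, spread, zero share, interval width or power for purchases, so no planned figure can be reproduced. Assumed grid: structural zero share π of 10–50%; mean of the non-zero part m of 5, 10 or 20 servings; and coefficient of variation c of the non-zero part of 0–1.0 (Poisson-gamma) or 0.5–2.0 (lognormal).

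**Step 1: fit to the outcome.** Nine servings over four weeks average 9/4 = 2.25, a value to which a negative binomial distribution gives no probability. Its variance is μ + αμ² and its zero probability is (1 + αμ)^(−1/α). The single α has to serve both.

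**Step 2: effect on the standard error.** With no true effect and n per arm, the model-based variance of the log mean ratio is 2(1/μ + α)/n. The actual variance is 2V/n, where V = Var(Y)/μ² and μ = (1 − π)m. For a Poisson-gamma non-zero part, V = (1 + c² + 1/m)/(1 − π) − 1. For a lognormal part the 1/m term drops out. The ratio of reported to actual standard error is √[(1/μ + α)/V].

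*Too wide:* Poisson-gamma, π = 0.3, m = 10, c = 0.7.
- The fitted α rises from 0.49 without structural zeros to 1.97 with them.
- μ = 7, so the model uses 1/7 + 1.97 = 2.11.
- The actual V is (1 + 0.49 + 0.1)/0.7 − 1 = 1.27.
- Ratio: √(2.11/1.27) = 1.29. Simulation gave 1.24 with 98% coverage. With 600–800 replicates the Monte Carlo error is about 1/√(2 × 700) = 2.7%, so the two are compatible.

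*Too narrow:* lognormal, π = 0.2, m = 10, c = 1.5.
- V = (1 + 2.25)/0.8 − 1 = 3.06.
- The actual standard error is √(2 × 3.06/112) = 0.234 (simulated 0.235).
- The model reports 0.182. The simulated ratio is 0.775, with 86% coverage.

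**Step 3: the wider grid.**

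| Set-up (all assumed) | Reported SE / actual SE |
|---|---|
| Poisson-gamma, c 0.5–0.7, m 10–20, zeros 20–30% | about 1.2–1.6 |
| Poisson-gamma, full grid, zeros 10–50% | 1.02–2.08 |
| Lognormal, zeros 10–30%, c 0.5 | 1.10–1.54 |
| Lognormal, zeros 10–30%, c 1.0 | 0.89–1.15 |
| Lognormal, zeros 10–30%, c 1.5–2.0 | 0.64–0.90 (coverage 80–93%) |
| Site SD 0, 0.1, 0.2, 0.3 on the log scale, ignored by the model (zeros 20%, m 10, c 0.7) | 1.23, 1.10, 0.93, 0.73 |
| Negative binomial mixed model with participant intercept, 20% or 30% of weeks zero | 1.17 or 1.31 |
| Same mixed model, 20% of participant-periods entirely zero | 0.60 |
| Robust SE, no site effects: Poisson-gamma; lognormal | 0.94–1.07; 0.88–1.07 |

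**Step 4: model or standard error?** With 190 participants, m = 20, c = 0.7, 20% zeros and a true mean ratio of 1.3, simulated power was 0.23 for negative binomial with model-based standard errors. It was 0.52 for negative binomial with robust standard errors and 0.52 for Poisson with robust standard errors. The miscalibration comes from the model-based standard error under misspecification, not from the estimated mean ratio.

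**The case against.** The strongest reply is that the plan commits to nothing. It says models will be considered and gives one by way of example, so two-part, hurdle and zero-inflated models all remain open. Some purchasing outcomes, such as number of trips, are true counts for which a count model is reasonable. A high share of zeros does not by itself defeat a negative binomial model: with m = 5, c = 1.0 and no structural zeros, 17% of values are zero and the ratio is 0.96. A four-week average among primary food shoppers may contain few zeros. The feasibility data in section 2.2 show skew in the share of food spending, which is not evidence of a zero share. The log-link alternative has no zero component either, and it also works on a ratio scale.

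Most of this stands, and it limits the point to a minor one. It does not rescue the example, which remains the only method named and suits neither excess zeros nor a continuous average. The last reply is met by stating one scale in advance and by robust standard errors, which do not need the variance model to be right.

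A reader might go further and infer that the fallback makes intervals too wide by some fixed amount such as 20–45%, costs Aim 2 much of its power and makes an inconclusive result likely. The documents do not support that. They supply none of the inputs and no standard-error type. Widening of that size appears only in a middle band of assumed values. Heavy tails, whole-period zeros or ignored site variation reverse the direction.

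**Conclusion.** The point holds as one of specification. The one model named has no zero component and is a count model, while the outcome is defined as a continuous, possibly non-integer average. Both facts follow from sections 5.2 and 17.3 without any simulation.

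The size of the consequence cannot be fixed from the documents. With model-based standard errors, the reported standard error is between about 0.6 and 2.1 times the actual one over the assumed grid. The shift from a difference to a ratio depends on the usual log link being used. Severity is minor: the outcome is secondary, the fallback is conditional, and the wording leaves better methods open. It is still worth settling before the data are seen.

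**What to change.** Replace the example in section 17.3 (Aim 2) with wording of this kind: *If zeros are frequent by a criterion stated in advance and judged on data pooled over arms, average weekly servings will be analysed with a two-part model (any purchase; amount if any) that retains the participant and site effects, and/or with a log-link model for the overall mean using site-clustered robust standard errors with a small-sample correction. The overall contrast in mean weekly servings will be reported on one pre-stated scale whichever model is used. Negative binomial or zero-inflated count models will be used only for counts such as number of trips.*

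Either scale can be chosen for the overall contrast. A difference can be recovered from a log-link or two-part fit by comparing the predicted means.

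The cost is a revised passage in the plan and slightly more analysis work, with no new data. The main downside is the correction needed with only 12 sites. The robust results above were obtained with independent participants, so they do not show how an uncorrected site-clustered standard error would behave.
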